4.4 Sample size calculation

The primary objective of the trial is to validate the prediction that a higher response (lower mean P-SCCAI score) is induced at T= 8 weeks by the prebiotics intervention in mild UC patients with low Bacteroidetes levels (predicted responders), but not in those with high Bacteroidetes levels (predicted non-responders) in their gut. Mild UC is defined as a P-SCCAI score of 3 to 5. According to an extensive study regarding UC disease activity conducted in the Netherlands, mild UC patients have a P-SCCAI score of 3.5 ± 0.5 (Mean \pm standard deviation (SD)), and patients in remission score at 1.0 ± 0.33 (Mean \pm SD)[34, 35].

In a series of germinated barley foodstuff (GBF) intervention studies, 10 mild to moderately active UC patients received 30 grams of GBF (equals to 10 grams fiber) daily for 4 weeks [4], and researchers found a significant decrease in clinical activity index scores. In a later study, another group of 11 mildly to moderately active UC patients consuming 20-30 grams of GBF (equals to 6.66-10 g fiber) daily for 4 weeks showed similar results, with decreases in clinical activity index scores [28].

Based on two-sided statistical testing for unpaired continuous data, an $\alpha=0.05$ (chance on type-I error) and $\beta=0.10$ (chance on type-II error), and assuming a 20% difference of mean P-SCCAI score between predicted responders with prebiotics and predicted non-responders with prebiotics, it was calculated that at least 11 subjects per group are needed for the primary outcome P-SCCAI ($\mu_1=3.5$; $SD_1=0.5$; $\mu_2=2.8$). According to previous trials on prebiotics on IBD patients, a 20% of drop-out rate is commonly seen. Given that the intervention duration is 8 weeks long, followed by a 1 year follow-up, higher dropout rate (30%) is expected. To compensate for a 30% drop-out rate, 15 subjects per group are needed.

To reach inclusion of 30 predicted responders and 30 predicted non-responders, we made an estimate how many subjects we need to screen based on the earlier obtained microbial composition of stool samples from UC patients in the Ede area. Around 50% of these subjects were categorized as low Bacteroidetes subjects (predicted responders) and while 17% of them as high Bacteroidetes subjects (predicted non-responders). To include these responders we will need to screen 177 mild UC patients.

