10.1 Primary study parameter(s)

Response (mean P-SCCAI score) between arms at T = 8 weeks

To assess the response, data of mean P-SCCAI score within each arm at T = 8 weeks (after the intervention) will be obtained.

Firstly, the mean P-SCCAI score between the predicted responders with prebiotics and predicted non-responders with prebiotics will be compared by using a Student T-test if normally distributed, otherwise a Mann-Whitney U test when skewed.

Secondly, the mean P-SCCAI score between prebiotics and placebo groups within predicted responders or predicted non-responders will be compared by using a Student T-test if normally distributed, otherwise a Mann-Whitney U test when skewed.

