10.2 Secondary study parameter(s)

Response over time

To assess the response over time, data of mean P-SCCAI score within each arm at T = 0, 4, 8, 12 and 60 weeks will be obtained. Comparisons will be made between groups (as done for T = 8 for the primary study parameter) as well as within subjects over time. With P-SCCAI score ≤ 2 being regarded as clinical remission, and a decrease in the P-SCCAI score by more than two points from baseline being regarded as clinical response, we will determine whether subjects have reached clinical remission and/or showed a clinical response over time.

To assess the response within each subject (clinical remission and/or clinical response) over time, data of sum P-SCCAI score within each subject at T = 0, 4, 8, 12 and 60 weeks will be obtained. For comparative analyses between baseline and intervention, the parametric paired sample T-test or the non-parametrical Kruskal-Wallis or Mann-Whitney

U test will be used, depending on the distribution of the samples. Differences between treatments before and after supplement intake will also be analysed by linear mixed models for repeated measures, using “treatment” [prebiotics/placebo], “responding” [responders/non-responders], “time point” [0, 4, 8, 12 and 60 weeks] and “treatment x responding x time point” as fixed effects and subject as random effect. Clinically relevant variables such as BMI, age, sex, and medication use will be taken into account.

Mucosal inflammation

Fecal calprotectin data will be analysed in the same manner as described above (Response over time).

GI complaints:

Data from GSRS will be computed into scores, and the score of each item will be pooled together as the sum score, and the score of each item within each domain will be pooled as well. All data will be analysed in the same manner as described above (Response over time). Differences over time within and between groups will be tested with mixed model analysis. Variables such as timepoint, group, age, sex will be taken into account.

Stool consistency and frequency

Average bowel movement per day and dynamic change on stool consistency will be calculated and collected. All data will be analysed in the same manner as described above (Response over time)..

Gut microbiota and SCFAs

Fecal SCFAs data will be analysed in the same manner as described above (Response over time)

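### The primary week-8 two-sample test gives no weight to randomised subjects without a week-8 score, although loss can be related to disease activity and earlier P-SCCAI scores are already collected

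*Protocol*

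**What the plan says.** Section 10.1 defines the data for the primary comparison: "data of mean P-SCCAI score within each arm at T = 8 weeks (after the intervention) will be obtained". Two sets of contrasts follow, each by Student t-test or, if the scores are skewed, Mann-Whitney U. The first is predicted responders against predicted non-responders, both on prebiotics. The second is prebiotics against placebo within each predicted group. No earlier score enters either test.

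Section 4.4 sizes the trial on a "20% difference of mean P-SCCAI score between predicted responders with prebiotics and predicted non-responders with prebiotics" and states that "it was calculated that at least 11 subjects per group are needed for the primary outcome P-SCCAI". It then adds: "To compensate for a 30% drop-out rate, 15 subjects per group are needed". The 30% is an increase over the 20% seen in earlier trials, and the reason given is the 8-week intervention followed by a year of follow-up.

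P-SCCAI is also collected at weeks 0, 4, 12 and 60 (8.1.2). Section 10.2 uses these scores in a secondary analysis: "Differences between treatments before and after supplement intake will also be analysed by linear mixed models for repeated measures". That model has treatment, predicted response, time point (0, 4, 8, 12 and 60 weeks) and their three-way product as fixed effects, with subject as random effect.

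A subject who reports an exacerbation of UC is withdrawn (8.4.1). Withdrawn subjects are not replaced (8.5) and, with an exception for some medical withdrawals, are not followed further (8.6).

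**The concern.** A two-sample test on the available week-8 scores is unbiased only if losing the score is unrelated to the course of disease. Under the protocol's own rules that is hard to assume. An exacerbation before week 8 leads to withdrawal, withdrawal generally ends data collection, and P-SCCAI measures the same disease activity. If subjects with high scores leave more often, the group doing worse loses more of its high scores, and the observed difference shrinks.

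The plan already holds information that could reduce this problem, namely each subject's week-0 and week-4 scores, but uses it only in the secondary analysis. At stake are some bias towards no difference, some loss of power in arms of 15, and the possibility that primary and secondary analyses give two different week-8 answers from the same trial.

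**Working it through.** **1. The plan's own figure.** Inputs from 4.4: means 3.5 and 2.8 (difference 0.7), SD 0.5, two-sided alpha 0.05, power 90%. The normal approximation gives

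n = 2 × [SD × (z₀.₉₇₅ + z₀.₉₀) / difference]² = 2 × [0.5 × (1.960 + 1.282) / 0.7]² = 10.72, rounded up to 11 per group.

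This matches the protocol. The 15 is reproduced as 11 × 1.3 = 14.3, rounded up.

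**2. What the week-8 test has left.** With 30% lost, 15 × 0.7 = 10.5 per arm remain, just under the planned 11. The power of the t-test (noncentral t, standardised difference 0.7/0.5 = 1.4) is then 86.0%. It is 90.6% at 20% loss and 93.8% at 10% loss.

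**3. Precision regained by using week 4.** If week 4 is observed in everyone and a share m is missing at week 8, unrelated to the scores, maximum likelihood behaves like a sample of

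n_eff = n(1 − m) / (1 − m·ρ²),

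where ρ is the week-4/week-8 correlation. The documents do not give ρ; 0.3 to 0.7 is assumed. For n = 15 and m = 0.3:

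| ρ | n_eff per arm | Power | Gain over 86.0% |
|---|---|---|---|
| 0.3 | 10.5 / 0.973 = 10.8 | 87.1% | 1.1 points |
| 0.5 | 10.5 / 0.925 = 11.4 | 88.8% | 2.8 points |
| 0.7 | 10.5 / 0.853 = 12.3 | 91.3% | 5.3 points |

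At 20% loss the model gives 91.1% to 93.4% against 90.6%; at 10%, 94.0% to 94.9% against 93.8%.

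**4. Bias when loss follows the week-4 score.** This is a large-sample simulation with SD 0.5 and true week-8 difference 0.70. Loss is logistic in the week-4 score and calibrated to the stated overall percentage. Assumptions not in the documents: log-odds 1 to 2 per point, correlation 0.5 to 0.7, week-4 difference between groups 0.35 to 0.7.

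| Overall loss | Completers' difference (true 0.70) |
|---|---|
| 10% | 0.67 to 0.70 |
| 20% | 0.65 to 0.70 |
| 30% | 0.64 to 0.69 |

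The lowest values come from the most extreme corner (log-odds 2, correlation 0.7, week-4 difference 0.7); at 30% loss a repeat of that corner gave 0.63. At 30% overall, loss is 33-42% in the worse group and 18-27% in the better one. Adjusting for week 4 returns 0.70, as it must when loss depends on week 4 alone.

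In simulated arms of 15 (correlation 0.3 to 0.7, week-4 difference 0.35, slopes 1 to 2 per SD of the week-4 score), completers gave 0.62 to 0.68 with 79-84% power. The variance of the completers' estimate was then 0.94 to 1.08 times that of the likelihood estimate. Under selective loss the gain is therefore mainly in bias; the power gain in step 3 belongs to random loss.

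**5. Bias when loss follows the week-8 state itself.** With the same SD, log-odds per point now on the week-8 score, and 30% loss, completers give 0.60 to 0.67 and the likelihood estimate 0.62 to 0.68. Using week 4 recovers only about 0.01 to 0.02.

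**The case against.** The strongest reply is that the effect is small and partly hypothetical.

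- **The 30% is not a week-8 figure.** It is justified by 8 weeks plus a year, so loss by week 8 is probably lower. This stands, which is why the range starts at 10%. A reader might infer that 30% will be missing at the primary time point; section 4.4 does not say so, although it applies the figure to this comparison.
- **The bias is within the noise.** With 10.5 per arm the standard error of the difference is 0.5 × √(2/10.5) = 0.22, so a bias of 0.06 (0.70 − 0.64) is about a quarter of one standard error. This stands. A shrinkage as large as 18% could be inferred, but that needs an SD of 1.5, which is not in the documents.
- **The protocol does not show that week 4 predicts drop-out or the week-8 score.** True: it gives no correlation and no drop-out model. What it does document is withdrawal on exacerbation, and step 5 shows that week 4 helps little if the flare comes without warning.
- **The 10.2 model is not ready to serve.** A reader might suppose that it can simply be promoted. It runs to week 60, has only a subject random effect and lists no two-way terms. A modified model is needed.
- **Handling of missing scores is often left to an SAP, which is not shown.** That the test uses only observed week-8 scores is inferred from the method and the absence of any imputation rule. The silence is no finding. The point is that the protocol itself fixes, as its primary method, a test that uses no other score.

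It would also be wrong to tie the 0.7 to prebiotics against placebo. Section 4.4 assumes it for responders against non-responders on prebiotics and gives no effect size for the placebo contrasts.

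**Conclusion.** The concern holds at a modest size. The primary test ignores subjects without a week-8 score, and the protocol's withdrawal and follow-up rules make it plausible that such loss is related to outcome. On the protocol's SD and difference, loss of 10-30% driven by the week-4 score would give about 0.64 to 0.70 instead of 0.70. At 30% random loss, using week 4 would recover about 1 to 5 power points. These figures rest on assumed correlations, drop-out slopes and week-4 differences, and 30% is an upper figure for week 8. The documents do not support a claim that the primary result would be seriously distorted, or that a mixed model would remove all the bias. Severity: minor to moderate. The case for changing is that a better use of data already collected costs little.

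**What to change.** In 10.1, take the week-8 contrasts (responders against non-responders on prebiotics, then prebiotics against placebo within each predicted group) from a likelihood-based repeated-measures model with:

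- P-SCCAI at weeks 0, 4 and 8 as outcomes and all randomised subjects included. Having baseline among the outcomes keeps subjects lost before week 4 in the analysis;
- the full arm-by-time interaction with all lower-order terms;
- an unstructured covariance over the three visits and small-sample degrees of freedom.

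Keep the two-sample t-test or Mann-Whitney U as a sensitivity analysis. Add a sensitivity analysis for subjects withdrawn because of a flare after week 4, for example by assigning them poor outcomes.

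Cost: no new visits, data or subjects. The model is a modified form of the one in 10.2 and must be written out in the protocol. It assumes approximate normality of a bounded integer score, which the Mann-Whitney fallback does not. It corrects only loss explained by observed scores, a weaker requirement than that of the completers' test but still an assumption. Subjects lost before week 4 contribute only their baseline score.

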2. OBJECTIVES

Primary Objective:

The primary objective is to validate the prediction that prebiotics intervention boosts butyrate production and thereby induces a higher response (lower mean Patient Simple Clinical Colitis Activity Index (P-SCCAI) score) in mild UC patients with low intestinal Bacteroidetes levels (predicted responders), but not in those with high intestinal Bacteroidetes levels (predicted non-responders) at T = 8 weeks

Secondary Objective(s):

1. To study the effects of the prebiotic intervention on response over time at T = 0, 4, 8, 12, and 60 weeks in mild UC patients
2. To study the effects of the prebiotic intervention on mucosal inflammation (fecal calprotectin levels) in mild UC patients
3. To study the effects of the prebiotic intervention on gastro-intestinal (GI) complaints (e.g., indigestion, abdominal pain) in mild UC patients
4. To study the effects of the prebiotic intervention on stool consistency and frequency in mild UC patients
5. To study the effects of the prebiotic intervention on the gut microbiota composition and SCFAs profile in mild UC patients
6. To study the effects of the prebiotic intervention on health-related quality of life in mild UC patients
7. To study the effects of the prebiotic intervention on medication use in mild UC patients
8. To study the effects of the prebiotic intervention on safety parameters in mild UC patients

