8.2 Randomisation, blinding and treatment allocation

During the screening period, participants will provide a fecal sample for microbiome signature measurement. This information will be used to assign subjects to four intervention arms by block randomization. All subjects screened for the trial will be assigned a unique participant ID number. Suitable participants will subsequently be randomised to prebiotics or placebo group using an online randomisation system accessible via password-protected access.

All sachets will be uniformly packaged to ensure double-blinding. Research teams and trial participants will be blinded to the treatment group for the duration of the trial. After collection of all laboratory & questionnaire data and performing all analysis of the baseline/intervention period the study (up to the 4-week follow-up; T=12 weeks) will be unblinded for the investigators. At the end of the study (T=60 weeks), the participants will be informed of the kind of intervention they received. (only when approved in the informed consent).

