8.3 Study procedures

A detailed description of procedures is shown in **Table 1**.

Table 1 Procedures

Page 1 of 1

Informed consent procedure

Informed consent procedure
One or more information meetings will be organized prior to the study. In this meeting, the investigators will explain the background, objectives and study procedures. During this meeting, there will be time for the potential research subjects to ask questions.

After the information event, subjects have two weeks to decide whether they are interested in participation or not. Research subjects who are willing to participate will receive the informed consent and the screening package which includes the P-SCCAI questionnaire and one stool collection kit. Then within one week, subjects will receive packages with corresponding products and instructions.

If COVID-19 restrictions are still in place, we would also provide the option of having online information meetings via Microsoft Teams (“Teams is designed and developed in compliance with the Microsoft Trustworthy Computing Security Development Lifecycle (SDL), <https://docs.microsoft.com/en-us/microsoftteams/teams-security-guide>”). No personal data will be collected or send via this route. If preferred, research subjects will always have the option to attend a physical meeting.

Screening

Subjects who fulfil all inclusion criteria and none of the exclusion criteria will be invited to a screening.

One stool sample will also be provided via the specific stool collectors (**Figure 4**). For female participants, pee gutters will also be provided to accurately separate stool from urine. After collection, stool material will be immediately frozen at the home freezers of the subjects, transported on dry ice (via courier) to the laboratory and subsequently frozen at -80 °C until further

Figure 4 Stool collector analysis. DNA will be isolated from part of the stool samples and subsequently be used for qPCR. Primers

targeting total bacteria and Bacteroidetes will be used to quantify the total gene copies and calculate the relative abundance of Bacteroidetes in the stool. Subjects that have a relative abundance of Bacteroidetes $\leq 10\%$ will be assigned to the predicted responders group, while those who have a relative abundance of Bacteroidetes $\geq 15\%$ will be assigned to the predicted non-responders group.

Baseline

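### The lead primary test, and the only one behind the sample size, compares two non-randomised groups that both take prebiotics; no primary test asks whether the prebiotic effect differs between strata

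*Protocol*

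**What the plan says.** Arms 1 and 2 are predicted responders (low Bacteroidetes) on prebiotics and placebo; arms 3 and 4 are predicted non-responders (high Bacteroidetes) on prebiotics and placebo.

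- **Objective (section 2).** The claim is differential: a lower week-8 P-SCCAI with prebiotics in predicted responders, "but not in those with high intestinal Bacteroidetes levels (predicted non-responders) at T = 8 weeks".
- **Primary analysis (10.1).** The first test is arm 1 v arm 3: "Firstly, the mean P-SCCAI score between the predicted responders with prebiotics and predicted non-responders with prebiotics will be compared". The other tests follow: "Secondly, the mean P-SCCAI score between prebiotics and placebo groups within predicted responders or predicted non-responders will be compared".
- **Sample size (4.4).** One contrast is used, "assuming a 20% difference of mean P-SCCAI score between predicted responders with prebiotics and predicted non-responders with prebiotics", with means 3.5 and 2.8, SD 0.5, two-sided alpha 0.05 and 90% power. This gives 11 per group, raised to 15 for 30% drop-out. No placebo mean is stated.
- **How the groups arise (8.2, 8.3).** The stratum follows from the stool qPCR result, at most 10% or at least 15% Bacteroidetes. Only the supplement is randomised: "Suitable participants will subsequently be randomised to prebiotics or placebo group using an online randomisation system".
- **Secondary analysis (10.2).** A mixed model over weeks 0, 4, 8, 12 and 60 includes a three-way term in treatment, predicted response and time point. It is not primary, is not covered in 4.4, and the listed terms include no two-way treatment by stratum term.

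**The concern.** Arm 1 v arm 3 compares two kinds of patient on the same product. Any difference in their week-8 course that has nothing to do with prebiotics goes straight into the result. The protocol gives reason to expect one: its introduction links low baseline Bacteroidetes to sustained remission after fecal microbiota transplantation, a different treatment, so the marker may reflect general outlook. A positive lead result could then be reported as validating the prediction although the product does nothing.

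The within-stratum tests are randomised, but a significant result in one stratum beside a non-significant result in the other does not test whether the two effects differ. The second half of the objective would rest on failing to find an effect with about 11 to 15 patients per arm. The question the trial was set up to answer is whether (arm 1 − arm 2) differs from (arm 3 − arm 4), and that is not a primary test.

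**Working it through.** **Inputs from section 4.4:** difference 3.5 − 2.8 = 0.7; SD 0.5; two-sided alpha 0.05; 11 completers per arm. Fifteen completers means no drop-out. Twelve is 15 × 0.8, from the remark that "a 20% of drop-out rate is commonly seen".

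**Assumptions, not in the protocol:** the week-8 prognostic gap between strata (0.2, 0.35, 0.5), an equal benefit in both strata (0.3 to 0.7), the placebo means, and SD 0.75 as a less favourable case.

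**1. The plan's own figure.** n = 2 × [0.5 × (1.960 + 1.282) / 0.7]² = 10.7, so 11 per group. It reproduces by the normal approximation; the exact t-test has 87.7% power at 11 and needs 12.

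**2. Lead test with an inert product.** Noncentral t, SE = SD × √(2/n), df = 2n − 2. Chance that arm 1 v arm 3 is significant:

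| Gap | SD 0.5, n = 11 | SD 0.5, n = 15 | SD 0.75, n = 11 |
|---|---|---|---|
| 0.2 | 15% | 18% | 9% |
| 0.35 | 35% | 46% | 18% |
| 0.5 | 61% | 75% | 32% |

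**3. All three results read together.** Call it the full pattern when arm 1 v 3 and arm 1 v 2 are significant and arm 3 v 4 is not. Simulation with 400,000 trials per scenario, SD 0.5, n = 11:

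- Inert product with the gaps above: 1.3%, 1.9%, 2%.
- Equal benefit of 0.4, 0.5 or 0.7 and no gap: 1.9%, 1.8%, 1.0%.
- A gap together with an equal benefit, so no true differential effect:

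| Equal benefit | n | Gap 0.2 | Gap 0.35 | Gap 0.5 |
|---|---|---|---|---|
| 0.3 | 11 | 7% | 13% | 17% |
| 0.4 | 11 | 9% | 16% | 22% |
| 0.5 | 11 | 8% | 15% | 21% |
| 0.5 | 15 | 8% | 14% | 18% |
| 0.7 | 11 | 4% | 7% | 9% |
| 0.7 | 15 | 2% | 3% | 4% |

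With SD 0.75, n = 11 and benefit 0.5 the figures are 5%, 9% and 14%. The interaction test is significant in the predicted direction in 2.5% of trials throughout.

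**4. What arm 3 v arm 4 can show.** 95% CI half-width: 2.086 × 0.5 × √(2/11) = 0.44 points; with 15 per arm, 2.048 × 0.5 × √(2/15) = 0.37. A true benefit of 0.35, half the planned 0.7, is non-significant in 65% of trials with 11 per arm and 54% with 15.

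**5. Power for the contrasts that answer the objective.** Interaction SE = SD × √(4/n), df = 4n − 4. With arm 1 at 2.8 and the other arms at 3.5:

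| SD | Contrast | n = 11 | n = 12 | n = 15 |
|---|---|---|---|---|
| 0.5 | arm 1 v 2 | 88% | 91% | 96% |
| 0.5 | interaction | 62% | 66% | 76% |
| 0.5 | both | 60% | 65% | 75% |
| 0.75 | arm 1 v 2 | 55% | 59% | 69% |
| 0.75 | interaction | 33% | 35% | 43% |

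If placebo responders reach 3.15 instead (SD 0.5), arm 1 v 2 has 35-46% power and the interaction 20-27%.

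**The case against.** The strongest reply is that randomised tests are already primary. Section 10.1 includes arm 1 v 2 and arm 3 v 4, and nothing says that success may be declared on arm 1 v 3 alone; being listed first is an order, not a stated hierarchy. Read together, the three results lead to a wrong conclusion in only 1-2% of trials with an inert product. That stands, and the 15-61% figures must be read as describing one test by itself.

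The remaining harm needs two assumptions at once, a prognostic gap and an equal benefit, and it shrinks to 4-9% (n = 11) or 2-4% (n = 15) if the equal benefit is the full planned 0.7. That also stands. For benefits of 0.3 to 0.5 with 11 per arm, however, the range is 7-22%, and no other primary result would reveal the error.

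The planned power would carry over to arm 1 v 2 if placebo responders also average 3.5. This is fair, but section 4.4 does not say so, and the power falls quickly if they improve. Likewise, the secondary mixed model could yield a week-8 differential effect, but it is neither primary nor powered.

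Finally, an interaction test with 62% power is a weak primary test. True, but the weakness lies in the design; leaving the test out does not remove it.

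**Conclusion.** The point holds. The contrast that leads the primary analysis and alone justifies the sample size is not randomised and cannot tell prediction from prognosis, and no primary test compares the prebiotic effect between strata. The within-stratum tests largely protect against an inert product being declared effective. They do not protect against an equal benefit being read as a differential one when the strata also differ in prognosis: about 4-22% of trials with 11 completers per arm and SD 0.5, over the gaps and benefits tried, against 2.5% for an interaction test. These rates rest on assumed gaps and benefits. The textual finding and the power figures at 0.7 and 0.5 use the plan's own inputs, plus the assumption that both placebo arms and arm 3 sit at 3.5. Because the trial exists to validate a predictive marker, this should be corrected before the data are analysed.

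**What to change.** In section 10.1:

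1. Make arm 1 v arm 2 (prebiotics v placebo in predicted responders) the lead primary test.
2. Second in a fixed sequence, test the week-8 treatment by stratum interaction from one linear model of all four arms.
3. Report arm 3 v arm 4 as an estimate with its 95% CI; neither its non-significance nor a significant interaction proves absence of effect in predicted non-responders.
4. Make arm 1 v arm 3 descriptive.

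In section 4.4, state the assumed placebo mean in each stratum and the week-8 SD, and give power for tests 1 and 2 as a range over completers and SD, as in the last table of the working.

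**Cost.** Wording only, with no added patients or data. The stated power becomes less favourable. In the best case (2.8 in arm 1, 3.5 elsewhere, SD 0.5) the chance of passing both tests is 60%, 65% or 75% with 11, 12 or 15 completers per arm, against 76%, 80% or 88% for the present three-result pattern. The interaction stays below 80% power at the planned size.

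Reaching 90% is not part of this change. It would take 22 completers per arm: 22/0.7 = 31.4, so 32 per arm and 128 randomised, and 64/0.17 = 376.5, so about 377 screened, against 60 and 177 planned.

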8. METHODS

8.1 Study parameters/endpoints

8.1.1 Main study parameter/endpoint

Response (mean P-SCCAI score) between arms at T = 8 weeks:

At T = 8 weeks (the end of the intervention), the P-SCCAI score will be collected via the P-SCCAI questionnaire. As main endpoint, the mean P-SCCAI score for each arm will be determined and compared to each other to determine the difference in response at T = 8 weeks.

P-SCCAI is derived from the original SCCAI questionnaire by translating into patients' comprehensible language, and has been validated to give substantial agreement with the original SCCAI [54]. P-SCCAI refers to disease symptoms during the previous week. It contains 13 items clustered into six domains: bowel frequency (during the day), bowel frequency (during the night), urgency of defecation, blood in stool, general well-being, and a number of defined extracolonic features of UC (i.e. arthritis, erythema nodosum, pyoderma angrenosum, uveitis).

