10. STATISTICAL ANALYSIS

Statistical analyses will be done using the statistical program embedded within R. The threshold for significance will be set at $p<0.05$, with a FDR correction for 16S rRNA gene sequence data. In general, the continuous data will be presented as mean \pm standard deviation or mean and interquartile range when skewed, and categorical data as counts and percentages. Normality will be checked by visual inspection and QQ plots, followed by the Shapiro Wilk test for testing if data show a normal distribution.

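### Three week-8 tests sit under the primary parameter at p<0.05 each; the first-listed and only powered one (arm 1 v 3) is not declared as lead or gate and is not a randomised comparison, so the familywise error can reach about 13%

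*Protocol*

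**What the plan says.** The arms are defined in Protocol section 3: predicted responders on prebiotics (1) or placebo (2), and predicted non-responders on prebiotics (3) or placebo (4).

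- **Section 10.1** gives the primary tests in two steps: "Firstly, the mean P-SCCAI score between the predicted responders with prebiotics and predicted non-responders with prebiotics will be compared" (arm 1 v 3), and then "Secondly, the mean P-SCCAI score between prebiotics and placebo groups within predicted responders or predicted non-responders will be compared" (arm 1 v 2 and arm 3 v 4). Each is a t-test, or a Mann-Whitney test if the data are skewed.
- **Section 10** sets one threshold: "The threshold for significance will be set at $p<0.05$, with a FDR correction for 16S rRNA gene sequence data". No correction is named for the P-SCCAI tests.
- **Section 8.1.1** describes the main endpoint only as "the mean P-SCCAI score for each arm will be determined and compared to each other".
- **Section 4.4** sizes the trial on one contrast, "assuming a 20% difference of mean P-SCCAI score between predicted responders with prebiotics and predicted non-responders with prebiotics", and gives the error rates as "Based on two-sided statistical testing for unpaired continuous data, an $\alpha=0.05$ (chance on type-I error) and $\beta=0.10$ (chance on type-II error").
- **Section 2** states the primary objective as a pattern: a lower score in predicted responders on prebiotics, and no such effect in predicted non-responders.

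The protocol does not make one of the three tests conditional on another, divide alpha between them, or turn the predicted pattern into a rule for success.

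**The concern.** Section 4.4 states a type-I error of 5%. That holds for a single primary test, or for several with a declared order or adjustment. Section 10.1 has three tests and neither safeguard, so as written a significant result on any of them could be presented as the primary finding. Discordant results have no agreed reading either. An example is arm 1 v 3 significant while arm 1 v 2 is not.

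Taking the first-listed test as the lead settles the error rate but not the interpretation. Arms 1 and 3 both receive prebiotics. They differ by baseline Bacteroidetes level, which is measured and not randomised. A week-8 difference between them could be a prognostic difference between strata and not a treatment effect.

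**Working it through.** **Inputs.** Threshold p<0.05 per test (section 10). Two-sided alpha 0.05, beta 0.10, means 3.5 and 2.8, SD 0.5, 11 per group before and 15 per group after the drop-out allowance (section 4.4). Three tests: 1 v 3, 1 v 2, 3 v 4 (section 10.1).

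**1. The plan's own figure.** n per group = 2 × [SD × (z₀.₉₇₅ + z₀.₉₀) / difference]² = 2 × [0.5 × (1.960 + 1.282) / 0.7]² = 10.7, so 11. The stated 11 is reproduced. With the exact t distribution, power at 11 is 87.7%. The calculation covers arm 1 v 3 only.

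**2. Error across the three tests.** Independent tests would give 1 − 0.95³ = 14.3%, but these tests share arms. With equal arm sizes, the test statistics correlate +0.5 (1 v 3 with 1 v 2), −0.5 (1 v 3 with 3 v 4) and 0 (1 v 2 with 3 v 4). Simulation of 400,000 trials with normal data, equal means in all four arms and two-sided t-tests gives:

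| False-positive event | 11 per arm | 15 per arm |
|---|---|---|
| Any of the three tests | 13.0% | about 13% |
| 1 v 3 or 1 v 2, either direction | 9.1% | 9.1% |
| 1 v 3 or 1 v 2, predicted direction only | 4.5% | 4.6% |
| Both 1 v 3 and 1 v 2, either direction | 0.9% | 0.9% |
| 1 v 3 significant, 1 v 2 not | 4.1% | 4.1% |

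For the third row the nominal rate of a single test is 2.5%. With Mann-Whitney tests on integer scores (assumed SD 1.5, 11 per arm), the first row becomes 11.8%.

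**3. Arm 1 v 3 as a measure of treatment effect.** Assume, for illustration only, that the strata differ at week 8 by 0.5 SD for reasons other than treatment. With no treatment effect at all, arm 1 v 3 is then significant in 20% of trials at 11 per arm and 26% at 15.

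**4. Power of the randomised alternatives (difference 0.7, SD 0.5, exact t).**

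- Arm 1 v 2: SE = 0.5 × √(2/n), which is 0.213 at 11 and 0.183 at 15. Difference/SE is 3.28 and 3.83. Power is 88% and 96%, the same as for arm 1 v 3.
- Difference of differences, (arm 1 − arm 2) − (arm 3 − arm 4): SE = 0.5 × √(4/n), which is 0.302 and 0.258. Difference/SE is 2.32 and 2.71. With 4n − 4 degrees of freedom, power is 62% and 76%, assuming the whole 0.7 is the interaction.

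**The case against.** The best defence is that a lead test can be identified. Section 10.1 lists arm 1 v 3 first, and section 4.4 spends its alpha and power on that contrast alone. If only that test counts, the primary error is 5%. A reader might infer from section 10.1 that the protocol has no order or lead at all, and the document does not support that. What remains is that being listed first and powered is not a gate: no text says that the other two tests are secondary to the first or depend on it.

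Secondly, the 13% is the most permissive count. It includes wrong-direction results and a benefit in arm 3 v 4, which would contradict the objective. Under a directional reading of the two relevant tests the figure is about 4.5% against 2.5%, and if both had to succeed it would be under 1%. This stands, so the 13% has to be quoted with its condition.

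Thirdly, gating may be set out in a statistical analysis plan that is not shown. That limits the point to the protocol. But the protocol itself fixes the primary tests and their threshold and names a correction elsewhere, and which contrast answers the primary objective is a protocol decision.

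Finally, moving the lead to arm 1 v 2 could look like a change of question, since success there is compatible with equal benefit in both strata. This is a fair limit on any remedy that stops at arm 1 v 2; the stratum contrast must also be tested before the prediction is called validated.

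**Conclusion.** The point holds in a conditional form. The protocol has three primary tests at 0.05 and an implied lead that is neither declared nor used as a gate. The familywise error reaches about 13% if any of the three can carry a primary claim, in either direction, with all four means equal. It is about 9% if only 1 v 3 and 1 v 2 count, and 5% if only the first test counts. A flat statement that this trial has a 13% false-positive rate would go beyond the document.

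Apart from the error rate, the implied lead compares two baseline strata on the same product, so by itself it cannot show that prebiotics caused the difference. The 20% to 26% illustration rests on an assumed 0.5 SD prognostic gap, for which the protocol gives no figure.

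Severity: should-fix. The primary claim is affected, but the repair is text only.

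**What to change.** **Section 10.1.** State a fixed sequence, each test at two-sided 0.05, stopping at the first non-significant result:

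1. Arm 1 v arm 2 at week 8, the randomised comparison in predicted responders.
2. The treatment-by-stratum difference of differences, (arm 1 − arm 2) − (arm 3 − arm 4).

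Report arm 1 v 3 and arm 3 v 4 with 95% intervals as supportive. State that success on (1) alone supports only an effect in predicted responders, and that the prediction in the primary objective is validated only if (2) also succeeds.

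**Section 4.4.** Restate the sample size for these two tests, using the power figures in the working.

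**If the sponsor keeps arm 1 v 3 as lead,** one sentence declaring it and gating the other two tests restores the 5% error rate, but not a randomised interpretation.

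**Cost.** The error control needs no extra patients. Later tests lose formal significance if an earlier one fails. The stated power for the full objective falls: it can be no higher than the 62% to 76% of the second test, against the 90% now planned for arm 1 v 3.
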